- (3) The intervention or procedure is likely to yield generalizable knowledge about the subjects' disorder or condition which is of vital importance for the understanding or amelioration of the subjects' disorder or condition

C. Pregnant Women and Fetuses

Provide justification for each of the following:

1. Where scientifically appropriate, preclinical studies, including studies on pregnant animals, and clinical studies, including studies on non-pregnant women, have been conducted and provide data for assessing potential risks to pregnant women and fetuses.

The research team will recruit pregnant and breast feeding women. Benefits from naloxone auto-injector outweighs the risks of opioid overdose death rather than the risk of congenital malformation due to naloxone. Additionally, pregnancy risk category of the naloxone is B.²¹ See definition below. Data on the excretion of naloxone in breast milk is unknown.

• Pregnancy category B:

Animal reproduction studies show no evidence of impaired fertility or harm to the fetus; however, no adequate and well-controlled studies have been conducted in pregnant women.

2. The risk to the fetus is caused solely by interventions or procedures that hold out the prospect of direct benefit for the woman or the fetus; or, if there is no such prospect of benefit, the risk to the fetus is not greater than minimal and the purpose of the research is the development of important biomedical knowledge which cannot be obtained by any other means.

Naloxone hydrochloride was administered during organogenesis to mice.

These studies demonstrated no embryotoxic or teratogenic effects due to naloxone hydrochloride. But benefits from naloxone auto-injector outweighs the risks of opioid overdose death rather than the risk of congenital malformation due to naloxone.

3. Any risk is the least possible for achieving the objectives of the research. Naloxone is only recommended for use during pregnancy when there are no alternatives and benefit outweighs risk. But, again, benefits from naloxone auto-injector outweighs the risks of opioid overdose death rather than the risk of congenital malformation due to naloxone.

D. Neonates of Uncertain Viability or Nonviable Neonates – not applicable for our study

Provide justification for each of the following:

- 1. Where scientifically appropriate, preclinical and clinical studies have been conducted and provide data for assessing potential risks to neonates.
- 2. Each individual providing consent is fully informed regarding the reasonably foreseeable impact of the research on the neonate.
- 3. Individuals engaged in the research will have no part in determining the viability of a neonate.
- 4. The research holds out the prospect of enhancing the probability of survival of the neonate to the point of viability, and any risk is the least possible for achieving that objective, or, the purpose of the research is the development of important biomedical knowledge which cannot be obtained by other means and there will be no added risk to the neonate resulting from the research

E. Nonviable Neonates - not applicable for our study

Complete this checklist if the subject population will include nonviable neonates. Provide justification for each of the following:

- 1. Where scientifically appropriate, preclinical and clinical studies have been conducted and provide data for assessing potential risks to neonates.
- 2. Each individual providing consent is fully informed regarding the reasonably foreseeable impact of the research on the neonate.
- 3. Individuals engaged in the research will have no part in determining the viability of a neonate.
- 4. The purpose of the research is the development of important biomedical knowledge that cannot be obtained by other means.

Verify each of the following:

5. Vital functions of the neonate will not be artificially maintained

False

- 6. The research will not terminate the heartbeat or respiration of the neonate True False
- 7. There will be no added risk to the neonate resulting from the research
 True
 False

F. Biomedical and Behavioral Research Involving Prisoners – not applicable for our study

1. Select and justify which allowable category of research involving prisoners this research falls within:

Study of the possible causes, effects, and processes of incarceration, and of criminal behavior, provided that the study presents no more than minimal risk and no more than inconvenience to the subjects

- Study of prisons as institutional structures or of prisoners as incarcerated persons, provided that the study presents no more than minimal risk and no more than inconvenience to the subjects
- Research on conditions particularly affecting prisoners as a class (for example, vaccine trials and other research on hepatitis which is much more prevalent in prisons than elsewhere; and research on social and psychological problems such as alcoholism, drug addiction, and sexual assaults)

Research on practices, both innovative and accepted, which have the intent and reasonable probability of improving the health or well-being of the subject

- Epidemiologic studies in which the sole purpose is to describe the prevalence or incidence of a disease by identifying all cases or to study potential risk factor associations for a disease, the research presents no more than Minimal Risk and no more than inconvenience to the subjects, and Prisoners are not a particular focus of the research.
- 2. Provide justification for each of the following regulatory criteria:
 - a) Any possible advantages accruing to the prisoner through his or her participation in the research, when compared to the general living conditions, medical care, quality of food, amenities and opportunity for earnings in the prison, are not of such a magnitude that his or her ability to weigh the risks of the research against the value of such advantages in the limited choice environment of the prison is impaired

- b) The risks involved in the research are commensurate with risks that would be accepted by nonprisoner volunteers
- c) Procedures for the selection of subjects within the prison are fair to all prisoners and immune from arbitrary intervention by prison authorities or prisoners. Unless justification is provided, control subjects must be selected randomly from the group of available prisoners who meet the characteristics needed for that particular research project
- d) The information is presented in language which is understandable to the subject population
- e) Adequate assurance exists that parole boards will not take into account a prisoner's participation in the research in making decisions regarding parole, and each prisoner is clearly informed in advance that participation in the research will have no effect on his or her parole
- f) When appropriate, adequate provision has been made for follow up examination or care after research participation, taking into account the varying lengths of individual prisoners' sentences, and for informing participants of this fact

III. Medical Devices – not applicable for our study

- A. Device Name:
- B. Manufacturer:

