Follow-up Visit (every three months): Obtain results of urine drug screening test, monitor frequency of naloxone auto-injector use, reason for naloxone auto-injector use, provide face to face education, as needed and refill naloxone auto-injector kit as needed. When patients report opioid overdose at these follow-up visits, we will obtain further information on the overdose via patient interview. The information will include date, time, and dose of naloxone use, clinical outcome [i.e., successful opioid reversal, death, and utilization of healthcare institution (e.g., EMS, emergency room, hospitalization)], to whom the kits were used, causality [i.e., type(s) of opioid], and call 911 after utilization of the kit. We will confirm the record by accessing PowerChart, only if patients used UNM Hospital for treatment.

Month 12 (1 Year): End of study visit: Obtain results of urine drug screening test, continue to ask same questions as in Follow-up visit.

If a patient uses the naloxone prior to the scheduled clinic visit, the study team will distribute one naloxone auto-injector carton prior to the next study visit. The study team will inquire about the circumstances for the use of the naloxone auto-injector.

Optional qualitative sub-study: If a study subject is selected as a potential candidate for the qualitative study, they may be contacted by phone or in person during one of their clinic visits and have the optional sub-study consent explained to them. If the person agrees to be interviewed, this will be done at a private consult room at ASAP. This visit may take 30-45 min at the end of which they will receive a \$20 gift card.

13.Data Analysis

Statistical Analysis

Statistical analysis will be performed using STATA (College Station Texas) and SAS version 9.3 (Cary, NC, United States).

The research team will collect the data and will use a descriptive analysis for demographic, social status, medical history, physical examinations, including vital signs (normal vs. abnormal findings), number of concomitant medications, scores of RIOSORD, and outcome related parameters listed in Section 12.

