The team will compare the monitoring parameters listed above to identify demographic data, epidemiological data, and correlations with the use of naloxone rescue kits. Differences between ASAP in categorical variables (utilization of naloxone auto-injector, utilization of EMX-run and emergency room visit during study period, gender, race, ethnicity, education level, marital status, results of physical examination [normal vs. abnormal], presence of substance abuse) will be tested by Chi Square test or Fisher exact test where appropriate. Differences in continuous variables (e.g., age, RIOSORD scores) will be tested by independent two samples, Student's *t* test, or Wilcoxon Rank Sum test, where appropriate. *P* values of less than 0.05 were considered statistically significant.

14. Provisions to Monitor the Data to Ensure the Safety of Subjects

In accordance with the IRB at UNM HSC, the investigators commit that the data will be used only for the research purpose. The data will be disclosed to all study investigators. The investigators will use PowerChart to obtain necessary information, such as past medical history, family history, and concomitant medications. The investigator will keep a patient log ("log book", Appendix 7) to track patients' consequent clinic visits. The investigators will use paper- and electronic-based data collection during their face-to-face interviews. All data will be transferred to REDCap system. The paper-based data and the log book will be stored in a locked cabinet in physician's office ([name]) at UNM ASAP. The paper- and electronic-based database and Excel file will be destroyed upon completion of data analysis. The study medication is stored in another locked cabinet of the same office. This room is also locked and only a few employees (charge nurse, study coordinator, PI, medical director) have access to open the room each day. Reported adverse reactions from naloxone for opioid overdose were tremor and hyperventilation associated with an abrupt return to consciousness.¹⁶ We will ask if study subjects experience withdrawal symptoms at their clinic visits. The frequency of these adverse reactions is unknown. These adverse reactions are not life-threatening, and hyperventilation will be managed with rescue breathing. This topic is included in patients' education in this study.

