- 4. Medical history (at initial visit only, Appendix 3: NINDS data collection format, modified).¹⁷
 - Past and current medical history.
- 5. Behavioral history (at initial visit only, Appendix 3: NINDS data collection format, modified).¹⁷
 - Smoking, alcohol, and illicit drug use
- 6. Family history (at initial visit only).¹⁷
 - Will only ask addiction-related diseases (i.e., history of alcohol abuse, substance abuse [prescription drug and illicit drug], and tobacco use)
- Vital signs (heart rate, blood pressure, respiratory rate, temperature, weight, height, Likert Pain Scale (0-10), Appendix 3, 4: NINDS data collection format, modified).¹⁷
- 8. Concomitant medications (Appendix 3: NINDS data collection format, modified).¹⁷
- 9. Urine toxicology screening test
 - Patients have urine toxicology screening test at each clinic visit (every week or every 2 or 3 months, which is dependent on patient's treatment regimen), as urine toxicology screening test is a part of standard care at UNM ASAP. If a patient does not have urine toxicology screening test done within 1 week prior to follow-up study visit, the research team will order the test.
- 10. Risk index for overdose or serious opioid-induced respiratory depression (RIOSORD,²⁰ Appendix 5)

Certificate of Confidentiality

This study has a certificate of confidentiality issued by the NIH that protects study

subject's privacy.

Location of data storage

All paper-based study data will be kept in a locked cabinet at UNM ASAP. Electronic data will be kept in a secured computer system in [name] office (UNM College of Pharmacy, Room B21B) and [name] office (Clinical Neuroscience Center or CNC). The computers are in their personal office behind a locked door, and the computer requires a password to open. The password for the office computer will not be shared with other people; thus, the data will be safely stored in PI's office at CNC and UNMCOP. Access to study databases is restricted to an as-needed basis. The investigators will use paper-based and electronic-based data collection when seeing the study subjects.

Duration of data storage

The data will be kept safely for 5 years, at which time [name] at ASAP will destroy all paper-based patient-relevant information with a shredder or put it in a confidential disposal box. The electronic data will be destroyed at the completion of data analysis.

Data access

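### Section 13 appears to test numeric vital signs and the 0-10 pain score only as normal vs. abnormal, with no stated cut-points, although a t test or Wilcoxon test on the measured values is already in the plan

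*Combined protocol and SAP*

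**What the plan says.** Three places in the protocol have to be read together.

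- **Collection.** Section 16 (Monitoring Parameters, item 7) lists "Vital signs (heart rate, blood pressure, respiratory rate, temperature, weight, height, Likert Pain Scale (0-10" and so places the pain score under vital signs.
- **Description.** The descriptive-analysis sentence of Section 13 includes "physical examinations, including vital signs (normal vs. abnormal findings" among the items to be summarised.
- **Testing.** The next paragraph of Section 13 compares the monitoring parameters and looks for correlations with kit use. Its categorical list contains "results of physical examination [normal vs. abnormal" and also "gender, race, ethnicity, education level, marital status"; these variables "will be tested by Chi Square test or Fisher exact test where appropriate". A separate sentence, "Differences in continuous variables (e.g., age, RIOSORD scores", assigns continuous variables to the t test or Wilcoxon rank sum test. It gives age and RIOSORD only as examples. The threshold is 0.05, with no adjustment mentioned.

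The text available gives no threshold for abnormal, no number of education levels and no trend test. The data-collection forms in Appendices 3 and 4 are not part of that text.

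**The concern.** Section 13 places vital signs inside the physical examination, gives them a normal/abnormal form, and then tests the physical examination in that same form. In the Section 16 list, vital signs are also the only examination-type data. The natural reading is that measured values will be reduced to two categories before testing.

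Two things would follow. A comparison of subjects who used a kit with those who did not would be less likely to show a real difference in any of these measures. The result would also depend on a cut that the plan does not state. Weight, height and a 0-10 pain score have no self-evident normal range, so that cut could be chosen after the data are seen.

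Education level raises a smaller question of the same kind: it is ordered, but neither named test uses the order.

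**Working it through.** The plan gives no power, cut-point or abnormal share for these comparisons, so there is no stated figure to reproduce. The abnormal shares and numbers of education levels below are assumptions, shown as ranges. Alpha is 0.05 (Section 13) and is taken as two-sided, since the plan does not state sidedness.

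**1. One cut on a normally distributed measure.** For a shift between two groups, the efficiency of the split relative to the t test is

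eff = φ(z)² / [p(1−p)],

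where p is the share called abnormal, z the matching normal quantile and φ the normal density. It does not depend on the ratio of group sizes.

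- p = 0.50: 0.3989² / 0.25 = 0.637, a loss of 36%.
- p = 0.20: 0.2800² / 0.16 = 0.490, a loss of 51%.
- p = 0.10: 0.1755² / 0.09 = 0.342, a loss of 66%.

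Against Wilcoxon, whose own efficiency is 3/π = 0.955, the loss at the median is 1 − 0.637/0.955 = 33%.

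**2. Effect on power.** If the t test has 80% power, the split has power Φ(2.802 × √eff − 1.96), where 2.802 = 1.960 + 0.842:

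- p = 0.50: 0.608
- p = 0.20: 0.500
- p = 0.10: 0.374

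**3. High and low values pooled as abnormal.** The efficiency for a shift becomes [φ(z_high) − φ(z_low)]² / [p(1−p)]. With 5% low and 15% high this is (0.2332 − 0.1031)² / 0.16 = 0.106. With equal tails it is 0, because a shift moves as many subjects out of one tail as into the other, to first order.

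**4. Non-normal measures.** For a median cut against the t test, efficiency is 4f(0)²σ². The loss is 18% for a logistic distribution and 4% for t with 5 df; for a Laplace distribution there is none. The 36% in step 1 is therefore not a general minimum. The distribution of the pain score is not given, so no figure is claimed for it.

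**5. Education level.** Assume a linear trend and a 1-df trend test with 80% power (noncentrality 7.85). The unordered chi-square with k − 1 df needs a larger noncentrality for the same power, and the loss is 1 − 7.85/λ:

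| Levels (assumed) | λ needed | Loss | Power left at the same n |
|---|---|---|---|
| 3 | 9.63 | 18% | 71% |
| 4 | 10.90 | 28% | 64% |
| 5 | 11.94 | 34% | 60% |
| 6 | 12.83 | 39% | 56% |
| 7 | 13.62 | 42% | 52% |

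**6. Cost of separate tests.** If one overall examination result is replaced by seven measures, each at an unadjusted 0.05, the chance of at least one false positive under independence is 1 − 0.95⁷ = 0.30, against 0.05 for one test. If the plan already intends a separate normal/abnormal test for each measure, this cost does not change.

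**The case against.** The strongest reply is that the plan never says vital signs are tested as binary. The phrase that mentions them is in a descriptive sentence, and the testing sentence names only the physical examination. The pain score does not appear in Section 13 at all; it is reached only through its place under vital signs in Section 16. The list of continuous variables is open, so numeric testing is allowed. All of this stands. A reader might infer that the plan commits itself to dichotomised tests, but the documents support only an implication. What remains is that normal/abnormal is the sole form stated for these measures and that no cut-point is given.

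A reader might also infer that at least a third of the information is lost throughout. That holds only for a normal measure cut once. It fails for some heavy-tailed distributions, cannot be asserted for a bounded pain score, and is wrong for education with three or four levels.

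On education, an unordered chi-square can detect non-monotone differences that a trend test would miss. Nothing in the documents shows that the relation is monotone, so the choice is a trade-off and not an error.

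Finally, Objective 2 is assigned to a logistic regression whose covariates and coding are not stated. It would go too far to say that this objective rests on dichotomised values.

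**Conclusion.** The point holds as a low-cost improvement to exploratory comparisons. Sections 13 and 16 together imply that seven numeric measures will be tested as normal vs. abnormal without stated cut-points. Even on the most favourable reading, their handling is left open.

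For a normal measure with a single cut and a shift between groups, the loss is 36% to 66% as the abnormal share goes from 50% to 10%. Pooling high and low values makes it worse; heavy tails or a discrete scale can make it smaller. These abnormal shares are assumptions.

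No stated endpoint depends directly on these tests, and the link to Objective 2 is indirect: it would matter only if the same coding were carried into the regression.

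**What to change.** In Section 13:

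- Name the pain score, blood pressure, heart rate, temperature, respiratory rate, height and weight among the continuous variables tested by t test or Wilcoxon.
- State that any of them used in the logistic regression enter as measured values.
- Keep normal/abnormal as a descriptive summary only, and state the cut-points used for it.
- Label these comparisons exploratory, since several unadjusted tests may replace one.

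Optionally, add a trend or rank test for education level, with the chi-square kept beside it. This helps only if the relation is monotone.

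The cost is a few sentences. No new data are needed, and the t test and Wilcoxon are already named. The one statistical cost is the larger number of unadjusted comparisons.

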Since April 2016, we have enrolled 358 patients at ASAP in our prospective nonrandomized clinical trial using the Evzio autoinjector. We have documented 82 overdose reversals thus far. Only one of the reported overdose reversals was from the study patients at ASAP, while the other 81 overdose reversals were from community members received naloxone from the study patients. For every 100 patients enrolled in the study, approximately 23 overdose reversals have been reported. We have submitted a peer-reviewed article about this data, and are now waiting to hear back regarding acceptance of the submission.

3. Study Design

- 3.1. The previous study at ASAP is a prospective observational study using the naloxone 0.4 mg auto-injector which took place April 4th, 2016 through April 30th, 2017.
- 3.2. Evaluation of patients enrolled include: # overdoses reversed, # naloxone doses needed, urine toxicology, history of overdoses witnessed, history of being reversed by naloxone, demographic information, medical history, etc.
- 3.3. For this current study, we propose the following new additional studies:
 - A biostatistical logistic regression analysis to study the characteristics of the study subjects who performed the overdose reversals (vs. the study subjects who did not).

8 | [Type text]

- A qualitative study to examine in-depth the characteristics of study subjects who a) documented many overdosed reversals/"saved" many community members, b) documented one overdose reversal/"saved" one community member, and c) did not document any overdose reversals
- Study the 2 mg Evzio autoinjector product to prospectively analyze the difference in doses (2 mg vs. 0.4 mg) needed to reverse an overdose. The goal will be to recruit 100 patients in one year and document between 20-30 overdose reversals in the community.

4. Inclusion and Exclusion Criteria

Inclusion Criteria

- A. All patients treated with naltrexone, methadone or buprenorphine as medication assisted treatment at the UNM Addiction and Substance Abuse Program (UNM ASAP) aged 18 or older.
 - Over 70% of patients at UNM ASAP on medication assisted treatment use methadone
- B. Subjects who sign a consent form.

Exclusion Criteria

- A. Subjects who are allergic to naloxone and its inactive ingredients.
 - Inactive ingredients: buffering agents
- B. Subject younger than 18.

5. Number of Subjects

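### Section 13 tests EMS and emergency-room use as a subject characteristic, but the visible text records it only as an outcome of a reported overdose, usually someone else's

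*Combined protocol and SAP*

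**What the plan says.** **Analysis (Section 13).** The team will look for "correlations with the use of naloxone rescue kits". Categorical variables, among them "utilization of EMX-run and emergency room visit during study period" (EMX is read here as EMS), "will be tested by Chi Square test or Fisher exact test where appropriate", and P "values of less than 0.05 were considered statistically significant". The sentence that introduces the list reads "Differences between ASAP in categorical variables (utilization of naloxone auto-injector" and continues through gender, race, ethnicity, education and marital status. It names no second group. It gives no denominator for the EMS/ER item and no coding rule for subjects who report no overdose.

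**Collection (Section 12, Follow-up Visit).** "When patients report opioid overdose at these follow-up visits, we will obtain further information on the overdose via patient interview". The information sought includes the clinical outcome of the overdose, and within it "utilization of healthcare institution (e.g., EMS, emergency room, hospitalization". It also covers who received the kit and whether 911 was called. The month 12 visit repeats the follow-up questions. PowerChart is used to confirm the record only where UNM Hospital gave the treatment.

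**Monitoring parameters (Section 16).** The list has no EMS or ER item asked of every subject.

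**Who was treated (Section 2, Year 1 ASAP Study).** "Only one of the reported overdose reversals was from the study patients at ASAP"; the other 81 of 82 were reversals of community members.

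**The concern.** The variable that is tested and the variable that is collected have different units. Section 13 treats EMS/ER use as something each subject has or lacks over the study period. Section 12 records it as something that happened after a particular overdose, and in the interim data the person concerned was almost always not the subject.

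Two consequences follow. A subject with no overdose to report is never asked, so the analyst must choose between 'no' and missing, and the plan does not say which. And a value that does exist describes the emergency care of the person treated, so reading it beside age or education as a trait of the subject would be wrong.

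At stake is how one line of the results table is read. A significant P value could reflect only the way the item was collected, while the more useful figure, how often a kit use is followed by emergency care, would not come out of this test.

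**Working it through.** **1. The plan's own rate.** Section 2 gives 82 reversals in 358 subjects: 82/358 = 22.9 per 100, which reproduces the stated figure of approximately 23. The full-year count in Sections 1 and 7 is 93 in 383: 93/383 = 24.3 per 100.

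**2. Subjects without a reversal.** If each reporter had exactly one reversal, (383 − 93)/383 = 290/383 = 75.7% would have none. Objective 3 expects some subjects to report many. With an assumed average of 2 reversals per reporter there are about 46 reporters and 337/383 = 88.0% have none; with 3, about 31 reporters and 352/383 = 91.9%. The Section 12 interview is triggered by a reported overdose, not a reversal. Overdoses reported without a reversal are not counted in the documents and would lower the share with no recorded value.

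**3. Performers versus the rest, non-reporters coded 'no'.** With k performers among n subjects and all x EMS/ER reports among performers, the two-sided Fisher p in the cases below is C(k,x)/C(n,x). Assume k = 93, n = 383:
- x = 2: (93×92)/(383×382) = 0.058
- x = 3: (93×92×91)/(383×382×381) = 0.014
- x = 9 (about 10% of performers): p = 2×10⁻⁶

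Three reports (3.2% of performers) are enough. If a proportion q of performers report EMS/ER use, the test rejects when X ≥ 3 with X ~ Binomial(93, q):
- q = 2%: 1 − (0.153 + 0.290 + 0.272) = 0.29
- q = 5%: 1 − (0.008 + 0.041 + 0.100) = 0.85
- q = 10%: 0.996

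With 46 performers, two reports suffice: (46×45)/(383×382) = 0.014. For the 2 mg target of 100 subjects, two of 20 performers give (20×19)/(100×99) = 0.038, and three of 30 give (30×29×28)/(100×99×98) = 0.025.

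**4. Performers versus the rest, non-reporters missing.** Only performers, and any subjects who reported an overdose they did not reverse, have values. Without a count of the latter, there is in effect no comparison group.

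**5. Dose cohorts (0.4 mg versus 2 mg).** With 383 and 100 subjects, equal overdose reporting (24.3%) and equal EMS/ER use per report (assumed values from 2% to 50%), simulated rejection at the 0.05 level was 1-4% (2,000 runs per value). Nothing is forced here. But the subject-level proportion is P(overdose reported) × P(EMS/ER given overdose). With the same assumed 50% EMS/ER use per overdose, reporting rates of 24% and 12% give 0.24 × 0.50 = 12% and 0.12 × 0.50 = 6% of subjects. A difference in reporting would look like a difference in emergency-care use.

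**The case against.** The strongest reply is that Section 13 never says performers are compared with non-performers. It names only ASAP, and kit use is itself one of the tested variables, so grouping by kit use would partly test kit use against itself. That stands: a reader might infer that the test result is built into the plan as written, and the documents do not support so much. The near-forced result needs both that grouping and a 'no' code for non-reporters. The stated interest in correlations with kit use makes the grouping plausible, not certain.

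A reader might also carry the problem into Objective 2. The documents do not support that either: Objective 2 is a logistic regression whose covariates are not listed, and EMS/ER use is not named as one.

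Nor do the documents establish that three quarters of subjects cannot be scored. The 93 in 383 counts reversals, not subjects who reported an overdose. And if the variable means overdose-related EMS/ER use, 'no' is a defensible value for a subject who was seen and reported no overdose. It remains true that the plan states no coding rule and that these zeros follow from the absence of a report.

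Finally, Appendices 3 and 4, which Section 16 cites for the outcome parameters, the visit figure and the protocol text just before the visible part of Section 12 were not available. An all-subject EMS/ER question could be there. Section 13 would then still have to say which of the two variables it tests. Section 12 does record who received the kit, and Section 13 plans a descriptive analysis of outcome parameters, so the data for a better summary are already foreseen.

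**Conclusion.** The mismatch between collection and test is real in the visible text, and it does not depend on how the groups are defined: the item is an outcome of an overdose, and in 81 of 82 interim reversals the person treated was not a study subject.

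The effect on the P value is conditional. With 93 performers against 290 others and non-reporters coded 'no', significance is reached from three EMS/ER reports, and the chance of it is about 85% if 5% of performers report any, but 29% if only 2% do. The number of distinct performers and the EMS/ER rates are assumptions. With dose cohorts the test keeps its level when overdose reporting is equal, but it does not separate reporting from emergency-care use.

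This is one variable in a list of univariate tests in a pilot study, and it is not one of the four endpoints. It is a cheap improvement, not a threat to the study's main conclusions.

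**What to change.** In Section 13, remove EMS run and emergency-room visit from the subject-level chi-square/Fisher list. Report instead the proportion of reported kit uses followed by EMS, an ER visit, hospitalization or a 911 call, overall and by strength. Count one overdose treated with a kit as one kit use, however many injectors were used. Label the results as outcomes of the person treated, and use intervals that allow for clustering of kit uses within subject, since some subjects will contribute several.

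If the subjects' own EMS/ER use is wanted as a characteristic, it needs a separate item. PowerChart alone would miss care given elsewhere and record it as 'no', so a variable drawn from it should be labelled as UNM Hospital care only.

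The cost is a sentence or two in Section 13 and a new denominator in one table, using information Section 12 already collects. The denominator falls to about 93 in Year 1 and 20-30 in Year 2, taking reversals as a stand-in for kit uses. At a proportion of 50%, the 95% half-width 1.96 × √(0.25/n) is about 10 percentage points for n = 93 and 18 to 22 points for n = 30 to 20, before any widening for clustering.
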